## Study Protocol and Statistical Analysis Plan

### BACKGROUND

#### *Sleep Duration and Sleep Quality in Spaceflight*

Adequate healthy sleep is essential in spaceflight to ensure astronauts maintain a high level of cognitive performance capability and do so without undue stress. However, studies have consistently found that chronic sleep restriction (i.e., sleep durations <6.5h) and astronauts' perceptions of poor sleep quality were common in spaceflight shuttle missions (Barger et al., 2014) and in International Space Station (ISS) missions (Barger et al., 2014; Jones et al., 2022). The latter study by Jones et al. (2022) yielded N=2,856 Reaction Self-Test (RST) assessments (i.e., RST = brief psychomotor vigilance test [PVT-B] with subjective ratings) that included n=394 evaluations pre-flight; n=2,109 evaluations in-flight; n=353 evaluations post-flight. This extensive study on N=24 astronauts on ISS for 6-month missions revealed that reductions in sleep duration and perceived poor sleep quality on ISS were associated with decrements in astronauts' performance on the brief psychomotor vigilance test (PVT-B) and increases in their perceptions of stress and physical exhaustion throughout the mission (Jones et al., 2022). Nearly half of the astronauts reported sleeping 6h/day or less on any given day in spaceflight, which is consistent with the earlier findings of Barger et al. (2014). When sleep duration on ISS was 6h or less per day, statistically significant deficits in PVT-B performance occurred (Jones et al., 2022). This result is consistent with Earth-based experiments showing that chronic restriction of sleep to 4h per night, 5h per night, or 6h per night resulted in sleep-dose-response cumulative psychomotor vigilance deficits, which involved statistically reliable decreases in PVT response speed and increases in lapses of attention, as well as deficits in cognitive speed and working memory performance (Dinges et al., 1997; Van Dongen et al., 2003; Belenky et al., 2003; Lim & Dinges, 2008; Mollicone et al., 2008), and increases in sleep propensity, evident in decreasing sleep latency (Carskadon & Dement, 1981). Importantly, these neurobehavioral performance deficits become progressively worse as sleep restriction to below 7h per day continued across consecutive days.

#### *Sleep Medication Use in Spaceflight*

Historically, NASA physicians have prescribed sleep medications to address sleep deficits in spaceflight, but among other concerns articulated by Barger et al. (2014), the use of hypnotic medications in space can pose a risk to astronauts' performance capability on awakening, especially in the event of an emergent awakening, that is, an emergency alarm requiring astronauts to perform at a high level within 30 seconds of the alarm. These concerns have been supported by a ground-based, double-blind, placebo-controlled study of zolpidem and zaleplon intake pre-sleep to assess their adverse effects on various cognitive tasks in N=34 astronauts, astronaut candidates, and flight controllers at NASA JSC (Johnston et al., 2015; Dinges et al., 2018). Results showed that pre-sleep ingestion of sleep medications, especially 10-mg zolpidem, posed a substantial risk to performance at emergent awakenings from sleep (Johnston et al., 2015; Dinges et al., 2018).

#### *SmartSleep Slow-Wave EEG Enhancement Could Mitigate Some of the Effects of Chronic Sleep Loss in Spaceflight*

There is a need for a technology that can improve sleep quality in space and biologically maximize the performance benefits of limited sleep duration, without unduly affecting the ability of astronauts to awaken abruptly due to an in-flight emergency. Studies have found that enhancement of EEG slow waves during sleep increased subsequent cognitive performance

(Bellesi et al., 2014; Bernardi et al., 2015; Ngo et al., 2013). Accumulating evidence suggests that many of the benefits of sleep are associated with sleep EEG slow waves. Slow waves reflect the near-synchronous alternation by millions of neurons between depolarized, active up-states, and hyperpolarized, inactive down-states that are thought to mediate the restorative effects of sleep on brain networks and cells (Tononi and Cirelli 2006). Sleep slow waves support system and synaptic consolidation by promoting specific patterns of neuromodulatory and electric activities. Subjective sleep quality is also related to the size and number of slow waves that occur nightly (Kecklund and Åkerstedt 1997).

Pharmacologic approaches to improve sleep by increasing slow waves are limited by issues of dependence and tolerance and are often associated with residual side effects during subsequent wakefulness (Feld et al. 2013). Moreover, pharmacological agents cannot be completely washed out of the metabolic cycle in cases where an individual, like an astronaut, is unexpectedly awakened from sleep and needs to function quickly and accurately.

SmartSleep is a new slow-wave enhancing technology that monitors and stages sleep electroencephalography (EEG) in real-time and delivers auditory stimulation during non-REM sleep in a closed-loop fashion at a volume that is dynamically modulated by sleep depth. Stimulation is stopped if the likelihood of sleep disturbance exceeds a conservative threshold. Pilot testing has indeed shown that the system can be used to increase the amount of slow waves occurring each night in a majority of individuals (Diep et al. 2020). Importantly, the increase in slow waves is correlated with the number of sub-awareness auditory tones played. SmartSleep consists of a sleep app and a headband worn during sleep that is comfortable and easily translatable for spaceflight.

**SmartSleep** offers an alternative to the dilemma of risking the adverse effects of chronic sleep restriction and low sleep quality in spaceflight, versus risking the adverse effects of medications on sleep and waking in ever-longer duration spaceflight. If increased amounts of slow-wave activity in sleep via SmartSleep can translate to cognitive performance benefits and/or sleep quality benefits, even during periods of chronically restricted sleep time to 5h/night, it will offer a significant advantage over the sleep medication alternative. If this is the case, it will also be essential to determine whether the enhanced slow-wave activity during sleep provided by SmartSleep will increase sleep inertia and thereby impair cognitive performance immediately following an emergent awakening. It is therefore imperative that the safety of increasing slow-wave activity be demonstrated to benefit subsequent waking cognitive performance while not exacerbating sleep-inertia performance deficits at emergent awakening. Operational safety needs to be demonstrated before the use of SmartSleep in the space program. Finally, to the best of our knowledge, a non-pharmacological slow-wave enhancing technology has not been tested in a chronic sleep restriction paradigm, despite the high prevalence of chronic sleep loss in astronauts and in the general population.

## OBJECTIVES

For the above reasons, we designed a double-blind, placebo-controlled laboratory study of SmartSleep to determine what effect it has on daytime cognitive performance and on emergent awakenings from sleep in a chronic sleep restriction paradigm (i.e., 5h/night for 4 nights). This study is the first to evaluate slow-wave activity enhancement and its effects on performance and sleep inertia during sleep using a chronic sleep restriction paradigm to do the following:

**Objective 1:** Evaluate whether slow wave sleep enhancement via the SmartSleep stimulus algorithms benefits daytime cognitive performance during a period of chronic sleep restriction as commonly observed during spaceflight. We assessed cognitive performance with the Cognition test battery (developed for NASA; Basner et al., 2015) across a range of cognitive domains and across a number of high fidelity spatial cognition tasks and space-operationally relevant tasks including Robotic On-Board Trainer (ROBoT); Six Degrees of Freedom Docking Simulator (6DF); and Lunar Landing Simulation.

**Objective 2:** Investigate whether SmartSleep slow-wave enhancement increases

performance decrements induced by sleep inertia after an emergent awakening.

**Objective 3:** Identify the best modality of acoustic stimulation in terms of slow-wave enhancement and cognitive performance among three different stimulation techniques: Continuous Fixed Interval (1 Hz, inter-tone interval stimulation), Block (5 seconds on versus 5 seconds off), and In-Phase Adjustable (constant stimulation with tones to be delivered during each upstate of the slow wave).

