## SPECIFIC AIMS

The overarching goal of this project is to mitigate the effects of chronic sleep loss by optimizing the SmartSleep technology and demonstrating its safety at the same time. It has the following Specific Aims:

**Specific Aim 1:** Determine whether slow-wave sleep can be enhanced via closed-loop auditory stimulation of EEG slow waves in healthy adult subjects using SmartSleep Headband technology, when sleep is restricted in duration to 5h per night over 4 consecutive nights.

Hypothesis 1: Slow wave sleep will be enhanced via closed-loop auditory stimulation of EEG slow waves relative to sham stimulation, when sleep is restricted in duration to 5h per night over 4 consecutive nights.

**Specific Aim 2:** Determine whether post-sleep cognitive performance functions sensitive to sleep restriction can be enhanced when SmartSleep closed-loop auditory stimulation is used on sleep-restricted nights relative to a sham SmartSleep control condition. Hypothesis 2: Daytime cognitive performance will be higher after closed-loop auditory stimulation of EEG slow waves relative to sham stimulation, when sleep is restricted in duration to 5h per night over 4 consecutive nights.

**Specific Aim 3:** Identify the acoustic stimulation modality with maximal benefits for slow-wave enhancement and daytime cognitive performance, when sleep is restricted in duration to 5h per night over 4 consecutive nights. Hypothesis 3: One of the three acoustic stimulation modalities enhances EEG slow waves significantly better than the other two modalities, and is also associated with enhanced cognitive performance during the daytime, when sleep is restricted in duration to 5h per night over 4 consecutive nights.

**Specific Aim 4:** Investigate systematic effects of consecutive nights of sleep restriction on slow-wave enhancement and daytime cognitive performance. Hypothesis 4: With increasing homoeostatic sleep drive induced by consecutive nights of sleep restriction, the observed slow-wave enhancement will mitigate some of the effects of chronic sleep loss on daytime cognitive performance.

**Specific Aim 5:** Assess any potential adverse effects of SmartSleep utilization during sleep restriction, especially related to sleep inertia after emergent awakening. Hypothesis 5: Cognitive functioning after emergent awakenings in the acoustic stimulation conditions will be non-inferior relative to sham stimulation based on a non-inferiority margin of 2 lapses on the PVT-B.

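### The modality named best under Aim 3 may have no non-inferiority result of its own on sleep inertia

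*Combined protocol and SAP*

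**What the plan says.** **Choosing a modality.** Objective 3 is to "Identify the best modality of acoustic stimulation in terms of slow-wave enhancement and cognitive performance". Specific Aim 3 is narrower: "Identify the acoustic stimulation modality with maximal benefits for slow-wave enhancement and daytime cognitive performance". Hypothesis 3 expects one modality to enhance slow waves better than the other two and adds that it "is also associated with enhanced cognitive performance during the daytime". The restriction to daytime comes from Aim 3 and Hypothesis 3; Objective 3 says only cognitive performance.

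**Sleep inertia.** This is handled separately, in Objective 2 and Aim 5. Hypothesis 5 reads "Cognitive functioning after emergent awakenings in the acoustic stimulation conditions will be non-inferior relative to sham stimulation", with a "non-inferiority margin of 2 lapses on the PVT-B".

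**Why both matter.** The Background says it will be essential to "determine whether the enhanced slow-wave activity during sleep provided by SmartSleep will increase sleep inertia", and that increased slow-wave activity must be shown to "benefit subsequent waking cognitive performance while not exacerbating sleep-inertia performance deficits at emergent awakening". The Specific Aims open with the goal of "optimizing the SmartSleep technology and demonstrating its safety at the same time".

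**Analysis.** The Statistical Approach makes PVT-B lapses the primary outcome, both after emergent awakenings and during the day. It fits a linear mixed model with a random subject intercept, modality at four levels, restriction night at four levels, and their interaction. Groups are compared post hoc if the type-III test is significant. It describes no non-inferiority analysis.

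**The concern.** The plan asks two questions about the same three modalities: which works best, and whether stimulation leaves people worse on abrupt waking. It wants both answered together, but no sentence joins them.

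Two gaps combine. Hypothesis 5 leaves open whether the margin applies to each modality or to stimulation as a whole. The analysis section supplies no confidence limit to set against the margin, and if the overall modality test is not significant it calls for no modality-against-sham comparison at all. A non-significant difference test does not show non-inferiority.

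The final report could then name one modality as best and make a general statement on sleep inertia, leaving the reader unable to tell whether that statement covers the named modality. For a device meant for crews who may be woken by an alarm, that is the combination the Background says has to be shown.

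**Working it through.** **1. The texts side by side**

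| Place | Criterion | Sleep-inertia term? | Unit |
|---|---|---|---|
| Objective 3 | slow waves, cognitive performance | none stated | one modality |
| Aim 3, Hypothesis 3 | slow waves, daytime cognition | no | one modality |
| Aim 5, Hypothesis 5 | post-awakening function, 2-lapse margin | yes | the conditions; each or overall not stated |
| Statistical Approach | difference tests, post hoc if type-III significant | lapses are primary, but no margin analysis | modality at 4 levels |

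No row makes the Aim 5 result part of the Aim 3 answer, and none guarantees a per-modality limit.

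**2. The plan's own power figure**

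Inputs from the Statistical Approach and Study Design: 12 subjects, effect 0.5, correlation 0.8, more than 80% power for SD below 0.9. Alpha is not stated; two-sided 0.05 is assumed.

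- SD of the paired difference = 0.9 × √(2 × (1 − 0.8)) = 0.569.
- Noncentrality = 0.5 × √12 / 0.569 = 3.04, with 11 df.
- Power = 79.1% at SD 0.90, 80.0% at 0.89 and 87.5% at 0.80.

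The figure reproduces if 0.9 is the SD of a single measurement. Taken literally as the SD of the difference, it gives 42.0%. Either way it is power to detect a difference in SD units. The documents give no power for the 2-lapse margin.

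**3. What a per-modality limit could show**

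The documents give no SD for the paired lapse difference, so 2, 3 and 4 lapses are assumed. A modality meets the margin if its upper one-sided 97.5% limit against sham is below 2. This uses a paired t with 11 df, critical value 2.201, and a true difference of 0.

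- Half-width = 2.201 × SD / √12.
- Largest observed difference that still passes = 2 − half-width.
- Noncentrality = 2 × √12 / SD.

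| Assumed SD | Half-width | Observed difference must be below | Noncentrality | Chance of passing |
|---|---|---|---|---|
| 2 | 1.27 | 0.73 | 3.46 | 88.3% |
| 3 | 1.91 | 0.09 | 2.31 | 55.8% |
| 4 | 2.54 | −0.54 | 1.73 | 35.3% |

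The mixed model would have somewhat more degrees of freedom. With one awakening test per restriction night there are 12 × 4 = 48 values, leaving 48 − 12 − 3 − 3 − 9 = 21 df. At the same SDs the chances become 91.0%, 59.6% and 37.9%, so the picture does not change.

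**The case against.** The strongest reply is that the safety information is not missing. Post-awakening lapses are part of the primary outcome, every subject is tested under every modality, and the model fits modality at four levels. Hypothesis 5 speaks of conditions in the plural, and no pooled stimulation-against-sham contrast is described anywhere. Identifying the most enhancing modality and reporting safety separately is a legitimate structure. All of this stands. What it leaves open is that a fitted factor is not a stated limit against a margin, and that pairwise comparisons depend on the overall test.

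Three stronger readings are tempting but not supported.

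- *The trial will recommend an unsafe modality.* The plan says identify, not recommend, and the Background says operational safety must be shown before use in the space program. It also poses a link between slow-wave gain and inertia as a question, so it is not established that choosing on slow-wave gain favours the worst modality.
- *A pooled test will hide a bad modality.* Pooling is one possible reading only. Its effect also depends on invented inputs. Excesses of 0.5, 1.0 and 4.0 lapses average 5.5/3 = 1.83, under the margin, but with a true mean of 1.83 a pooled test would pass in only about 3% to 7% of trials (SD 2 to 4, correlation among the three differences 0 to 1). A more lopsided assumption (+3, 0, 0, with the first modality also best on benefit) gives 49%, 25% and 16% for that modality being both chosen and covered by a pooled pass, at SD 2, 3 and 4. Neither says what would happen in this trial.
- *Failing the margin must bar a modality from being named best.* With 12 subjects that is a trade-off: at the larger assumed SDs such a rule would often exclude a modality that is truly equal to sham.

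**Conclusion.** The concern holds as a gap in linkage and specification. Aim 3 and Hypothesis 3 choose on slow-wave gain and daytime cognition; Hypothesis 5 does not fix its unit; the analysis section contains no non-inferiority comparison and makes pairwise contrasts conditional. The modality named best may therefore carry no non-inferiority result of its own, contrary to the plan's stated wish to show benefit and safety together. That conclusion rests on the text alone and needs no assumed figures.

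The practical size cannot be derived, because the documents give no lapse data. The 88%, 56% and 35% above rest on assumed SDs, a true difference of zero and a one-sided 97.5% limit. They show how informative a per-modality limit would be with 12 subjects, not how often a wrong conclusion would be drawn.

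**What to change.** 1. **Hypothesis 5.** Word it for *each* acoustic stimulation condition against sham, keeping the plan's 2-lapse margin.
2. **Statistical Approach.** From the existing mixed model, estimate each modality-minus-sham difference in post-awakening PVT-B lapses, with a confidence limit at a pre-stated level, whatever the type-III result, and compare it with the margin. State how the three comparisons are handled and what precision 12 subjects are expected to give.
3. **Reporting of Aim 3.** Set these limits beside the Aim 3 result. Describe a modality as both best and non-inferior on sleep inertia only if its own limit lies within the margin. Otherwise report it as *enhancing, non-inferiority on sleep inertia not shown*.

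**Cost.** A short paragraph of text, with no new subjects, data or threshold, since the test is already given on every restriction night. The limits may be wide, and possibly no modality will meet the margin; the report would then have to say so. The document describes the study in the past tense, so if lapses by modality have already been examined, the analysis should be labelled post hoc.

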## SPECIFIC AIMS

The overarching goal of this project is to mitigate the effects of chronic sleep loss by optimizing the SmartSleep technology and demonstrating its safety at the same time. It has the following Specific Aims:

**Specific Aim 1:** Determine whether slow-wave sleep can be enhanced via closed-loop auditory stimulation of EEG slow waves in healthy adult subjects using SmartSleep Headband technology, when sleep is restricted in duration to 5h per night over 4 consecutive nights.

Hypothesis 1: Slow wave sleep will be enhanced via closed-loop auditory stimulation of EEG slow waves relative to sham stimulation, when sleep is restricted in duration to 5h per night over 4 consecutive nights.

**Specific Aim 2:** Determine whether post-sleep cognitive performance functions sensitive to sleep restriction can be enhanced when SmartSleep closed-loop auditory stimulation is used on sleep-restricted nights relative to a sham SmartSleep control condition. Hypothesis 2: Daytime cognitive performance will be higher after closed-loop auditory stimulation of EEG slow waves relative to sham stimulation, when sleep is restricted in duration to 5h per night over 4 consecutive nights.

**Specific Aim 3:** Identify the acoustic stimulation modality with maximal benefits for slow-wave enhancement and daytime cognitive performance, when sleep is restricted in duration to 5h per night over 4 consecutive nights. Hypothesis 3: One of the three acoustic stimulation modalities enhances EEG slow waves significantly better than the other two modalities, and is also associated with enhanced cognitive performance during the daytime, when sleep is restricted in duration to 5h per night over 4 consecutive nights.

**Specific Aim 4:** Investigate systematic effects of consecutive nights of sleep restriction on slow-wave enhancement and daytime cognitive performance. Hypothesis 4: With increasing homoeostatic sleep drive induced by consecutive nights of sleep restriction, the observed slow-wave enhancement will mitigate some of the effects of chronic sleep loss on daytime cognitive performance.

**Specific Aim 5:** Assess any potential adverse effects of SmartSleep utilization during sleep restriction, especially related to sleep inertia after emergent awakening. Hypothesis 5: Cognitive functioning after emergent awakenings in the acoustic stimulation conditions will be non-inferior relative to sham stimulation based on a non-inferiority margin of 2 lapses on the PVT-B.

[figure not shown]
## METHODS RELATED TO SPECIFIC AIMS

### *SmartSleep Technology*

The SmartSleep technology uses two small sensors in the headband to continuously detect the brain's slow wave sleep (delta/theta frequency) in real time, and a closed-loop algorithm customizes the timing and volume of tones to optimize the sleep pattern. Thus, the device uses "quiet audio tones" (sub-awareness) to increase slow waves, which can enhance sleep quality/depth, thereby enhancing subsequent waking cognitive performance without the unwanted sedating effects of medications on cognitive functions during emergency awakenings. Philips completed commercial development of the SmartSleep technology (<https://www.usa.philips.com/c-e/smartsleep-advocacy.html>). The Philips SmartSleep website states that SmartSleep is a, "Wearable sleep headband and mobile app clinically proven to improve the quality of your sleep", and that it "increases your energy in the same sleep time", it is

“for people who typically sleep <7 hours per night”, and it is a “drug-free sleep enhancement technology.”

There is evidence that it is possible to enhance slow waves through non-pharmacological means, particularly with auditory stimulation (Bellesi et al., 2014; Tononi et al., 2010; Ngo et al., 2015; Ngo et al., 2013; Papalambros et al., 2017). The enhanced slow waves are indistinguishable from spontaneous ones in shape, origin, distribution, and propagation (Riedner et al., 2011).

**Figure 1. a)** The presence of EEG patterns (high power in the alpha 8-12 Hz and/or beta 15-30 Hz bands) indicative of (micro) arousals is first evaluated. If arousal-like activity is detected in the EEG during stimulation, the stimulation stops. If the arousal-like activity is detected outside the stimulation period, the onset of the next stimulation period is delayed. If no arousal-like activity is detected, then the system attempts to detect deep sleep based on slow wave activity (SWA) and the temporal density of detected slow-waves. On detection of sufficiently deep sleep, the auditory stimulation is delivered. **b)** Enhancement of slow waves when stimulation is delivered. **c)** SWA enhancement due to stimulation. The green markers indicate the time at which the stimulation was delivered

In the last few years, Philips in collaboration with the University of Wisconsin-Madison, have developed a closed loop, real-time, embedded, and sleep wearable system that monitors sleep EEG and delivers auditory stimulation during deep sleep (N3) at a volume that is dynamically modulated by sleep depth. Sleep depth is estimated by taking the ratio between the EEG power in the 0.5 to 4 Hz band and the power in the 15 to 30 Hz band. The system consists of a headset

with a single dry EEG electrode placed on the forehead and an integrated processing unit embedded in the headband (Figure 1a). The reference electrode is positioned on the right mastoid with conductive gel to improve impedance. This system focuses on the detection of deep sleep (N3) and wakefulness such that it targets the stimulation to periods where sleep is deep and stimulation related disturbance is prevented. The N3 (wake) detection sensitivity and specificity are 73.5% (76.4%) and 96.9% (82.5%), respectively. The stimulation is delivered through speakers in a headset in the form of 50-millisecond audible tones with a one-second inter-tone interval. As reported in several publications (Ngo et al., 2013; Papalambros et al., 2017; Santostasi et al., 2015), the slow-wave activity (SWA) enhancing effect is optimized by synchronizing the first tone to the up-phase of a detected slow-wave. If the likelihood of sleep disturbance exceeds a pre-established threshold, the stimulation is stopped.

At this point, it is unclear which acoustic stimulation paradigm produces the best results in terms of slow-wave enhancement and cognitive performance improvement. In this study, we will systematically compare three acoustic stimulation modalities and sham. The four stimulation modalities will be provided by Phillips and are as follows:

- Continuous Fixed Interval: 1 Hz inter-tone interval stimulation
- Block: 5 seconds on versus 5 seconds off, and
- In-Phase Adjustable: constant stimulation with tones to be delivered during each upstate of the slow wave.
- Sham: No auditory stimulation while wearing the SmartSleep headband

The slow wave amplitude enhancement produced by the auditory stimulation is shown in Figure 1b. The amplitude of deep sleep EEG clearly increases when the auditory stimulation (indicated by the green vertical lines in Figure 1b) is delivered. An illustration of SWA enhancement is shown in Figure 1c where the black curve is the SWA of a sham sleep session (without stimulation but while the device is worn) and the pink curve is the SWA of a sleep session with stimulation. The green markers (i.e., tone location) indicate the periods where the stimulation was delivered.

A previous version of SmartSleep was tested in a study supported by the Australian Cooperative Research Center for alertness, safety and productivity. The results of this study (Diep et al., 2020) demonstrated that >65% of participants exhibited enhanced slow wave energy in the stimulation condition (STIM) with an average of 28.4% increase with respect to sham. Furthermore, large effect sizes were observed for improved executive function (Verbal Fluency) and morning vigilance (PVT) following stimulation relative to sham.

